## 6.2 Milestones and Timeline for DUS2

DUS2 will be conducted after the implementation of changes to the summary of product characteristics (SmPC) and the follow-up communication activities with health care professionals. Anticipated timelines submitted to the EMA have been revised by the research institutions. The original and revised timelines for completing DUS2 are presented in the table below.

Timelines for finalising the study report in THIN, IACS, SIDIAP, and the Sweden databases have been confirmed by the researchers at each of these data sources. In THIN, the final report is planned to be finalised by 31 December 2015. In IACS, SIDIAP, and Sweden the final report is planned to be finalised by 30 September 2016. In Germany, the original timelines have been adapted based on experience from the implementation of DUS1. The analysis is expected to be completed by 1 November 2016, and the final report incorporating the cumulative results from all the data sources is expected to be completed for submission to the MHRA by 1 February 2017. This is about 1 month later than the originally planned date of completion.

Milestone	Anticipated Date	Revised Date
Approval SmPC changes	May 2013	May 2013
SmPC implementation period	May 2013 - Nov 2013	Jun-Dec 2013
Patient accumulation – 1 year	Nov 2014	1 Jan 2014 – 31 Dec 2014
Data availability – THIN	May 2015 a	1Q 2015 b
Start of data collection c – THIN	2Q 2015	1 Apr 2015
End of data collection d – THIN	3Q 2015	30 Jun 2015
Final report – THIN	4Q 2015	31 Dec 2015
Data availability – IACS, SIDIAP, Sweden e	3Q 2015-1Q 2016	Jan 2016
Final report – IACS, SIDIAP, Sweden	2Q 2016-3Q 2016	30 Sep 2016
Data availability – GePaRD f	1-2Q 2016	1 Jul 2016
Final report – THIN, IACS, SIDIAP, Sweden, and GePaRD g	3-4Q 2016	1 Feb 2017 h

EU PAS Register = European Union electronic register of post-authorisation studies; GePaRD = German Pharmacoepidemiological Research Database; IACS = Aragón Health Sciences Institute; SIDIAP = Information System for the Advancement of Research in Primary Care database, Catalonia, Spain; THIN = The Health Improvement Network, United Kingdom.

Note: Timelines revised by IACS, IDIAP, Karolinska, and BIPS in March 2014. Contracts between sponsor and research organisations and approvals by data protection, data custodian, ethics committees, and scientific review bodies are pending. Timelines may be impacted by duration of contract reviews, approvals of mentioned bodies, and availability of data and staff at research institutions once contracts and approvals are finalised.

a Based on 6 months' lag time for data availability after patient accumulation.

b Based on communication with THIN.

c Date from which data extraction starts.

d Date from which the analytical data set is completely available.

e Based on 12 months' lag time for data availability after patient accumulation.

f Based on an expected 18 months' lag time for data availability after patient accumulation.

g Conditional to data availability.

h Final report ready for submission to the MHRA.

## 7 Rationale and Background

We present a study protocol for conducting a drug utilisation study on the use of cilostazol in several European populations in the context of the European Medicines Agency (EMA) cilostazol referral under Article 31 of Council Directive 2001/83/EC.

Cilostazol has been marketed in Europe for intermittent claudication since 2002. The EMA has recently reviewed cilostazol (Pletal, Ekistol) for intermittent claudication, prompted by a referral under Article 31 of Council Directive 2001/83/EC. The focus of the review was the role of cilostazol in current treatment of intermittent claudication and the balance of risks and benefits of the drug. The preliminary Joint Assessment Report (4 July 2012) recommended the conduct of a drug utilisation study (DUS) using database sources to understand the characteristics of users of cilostazol, duration and patterns of cilostazol use, and the prevalence of concomitant use of cilostazol and other drugs with which it may interact.

Prior research conducted in the region of Cantabria in Spain showed that 70% of users of cilostazol were elderly patients with underlying comorbidities who were treated concurrently with several other medications in addition to cilostazol (González-Ruiz et al., 2011).

The plan is to conduct the DUS in two phases. DUS1 will evaluate cilostazol as currently used in several European countries during the period from launch through 2011. DUS2 will be conducted after the implementation of changes to the summary of product characteristics (SmPC) and the follow-up communication activities with health care professionals (HCPs) and will evaluate the impact of these measures during the year 2014 in the same countries as DUS1. DUS2 will be conducted using the same protocol as DUS1. Both DUS1 and DUS2 will include all the marketed products containing cilostazol in the countries, irrespective of brand.

This protocol describes the study design and methods for conducting DUS1 and DUS2. The study is proposed to be conducted in populations covered in automated health databases from four European countries: Spain, the United Kingdom (UK), Germany, and Sweden. Adjustments may be made to the protocol after DUS1 is completed.

## 8 Research Question and Objectives

The primary objectives of the DUS are as follows:

- To describe the characteristics of new users of cilostazol according to the following factors:
  - Demographics (e.g., age and sex)
  - Baseline comorbidity including conditions listed in the SmPC and the risk management plan (RMP) as potential or identified safety concerns (Otsuka Pharmaceutical Europe Ltd, 2012).
  - Baseline and concurrent use of medications potentially interacting with cilostazol and other medications

- Specific comorbidity and use of medications considered in the proposed risk minimisation measures, specifically those included in the proposed changes to the SmPC
- To describe the duration of the use of cilostazol and discontinuation patterns

Secondary objectives of the DUS are as follows:

- To quantify and describe off-label prescribing
- To describe dosage patterns of the use of cilostazol
- To assess the proportion of patients who are hospitalised for any cause while treated with cilostazol
- To describe the medical specialties of physicians prescribing cilostazol

The study objectives are the same for DUS1 and DUS2. DUS1 provides the baseline characteristics of users of cilostazol before the implementation of SmPC changes and communication with HCPs. DUS2 will be conducted after the implementation of these measures to evaluate their impact on the prescribing of cilostazol.

## 9 Research Methods

### 9.1 Study Design

The DUS is a cohort study of new users of cilostazol identified in five proposed European population-based automated health databases from four countries:

- The Aragón Health Sciences Institute (Instituto Aragonés de Ciencias de la Salud [IACS]) database, Spain
- The Information System for the Advancement of Research in Primary Care (Sistema d'Informació per el Desenvolupament de la Investigació en Atenció Primària [SIDIAP]) database in Catalonia, Spain
- The German Pharmacoepidemiological Research Database (GePaRD ), Germany
- The Health Improvement Network (THIN), United Kingdom (UK)
- The Swedish National Databases.

[figure not shown]
Study participation

- THIN has agreed to provide the data for conducting the study. The THIN Scientific Review Committee approved the study in February, 2013. IACS, SIDIAP, GePaRD and Sweden confirmed interest in participating in the study. The principal investigator in IACS will be [name] [name].
- Conduct of the study in the GePaRD needs approval by the statutory health insurance providers (SHIs) to send individual patient-level data to BIPS to be used in the analysis.
- A detailed description of these databases is included in Section 9.4.

New users of cilostazol will be characterised in terms of demographics, comorbidity, and past and concurrent use of medications before and after receiving the first prescription

for cilostazol (start date) according to the time frame displayed in Figure 1. Comorbidity for each patient will be assessed for the whole medical history available in each database before the start date. Conditions and procedures that will be used to evaluate the risk minimisation measures based on changes in the SmPC (contraindications, posology, and warnings and precautions) will be assessed for the 6 months before the start date. Comedications will be evaluated for the 6 months before the start date. Concurrent use of potentially interacting medications will be assessed for the 3 months before the start date and during follow-up. Duration of use of cilostazol will be assessed during follow-up.

**Figure 1. Overview of Study Design**

## 9.2 Setting

### 9.2.1 Source Population

The source population includes all individuals registered in the study databases since the date of the first recorded prescription of cilostazol in each database.

### 9.2.2 Study Period

The study period is defined in each database as the time between the date when cilostazol became available in the corresponding country and the latest date of data availability (Table 2). The estimated end of study period for IACS, GePaRD, and Sweden will be 31 December 2011. Partial data for the year 2012 are expected to be available in SIDIAP and THIN.

**Table 2. Estimated Study Period in Each Study Database**

	IACS, Spain	SIDIAP, Spain	GePaRD, Germany	THIN, UK	National Databases, Sweden
Cilostazol launch in country a	Jun 2009	Jun 2009	Jan 2007	Jun 2002	Apr 2008
Study period (based on cilostazol launch date and data availability, end of 2012 or early 2013)	Jan 2010 – Dec 2011	Jun 2009 – Apr 2012	Jan 2007 – Dec 2011	Jun 2002 – Dec 2012	Apr 2008 – Dec 2011

[figure not shown]
GePaRD = German Pharmacoepidemiological Research Database; IACS = Aragón Health Sciences Institute; SIDIAP = Information System for the Advancement of Research in Primary Care database, Catalonia, Spain; THIN = The Health Improvement Network, United Kingdom; UK = United Kingdom.

a Provided by Otsuka.

### 9.2.2.1 Study Period for DUS2

The study period for DUS 2 is from 1 January 2014 to 31 December 2014, following the implementation of changes to the summary of product characteristics (SmPC) and communication activities with HCPs that took place during 2013 (Figure 2).

**Figure 2. Study Period for DUS 1 and DUS 2 in Relation to 2013 SmPC Changes**

DUS 1 = first drug utilisation study; DUS 2 = second drug utilisation study; SmPC = summary of product characteristics.

### 9.2.3 Study Cohort

The study cohort includes all individuals from the source population who have a first recorded prescription of cilostazol during the study period and have been continuously enrolled in the database for at least 6 months. For each patient, the **start date** is defined as the date a patient receives a first prescription for cilostazol after 6 months of continuous enrolment in the database (see Section 9.2.4, Inclusion Criteria). Because the study period starts at the year cilostazol was available in each country, members of the study cohort are new users of cilostazol. For DUS2, the study cohort includes all individuals from the source population who have a **first ever** recorded prescription of cilostazol during the study period and have been continuously enrolled in the database for at least 6 months.

#### **9.2.4 Inclusion Criteria**

Members of the study cohort are required to have been continuously enrolled in the study database for an eligibility period of at least 6 months before the start date. This ensures that all patients will have at least 6 months of information recorded in the database.

#### **9.2.5 Exclusion Criteria**

Because the DUS seeks to characterise all new users of cilostazol, no exclusion criteria regarding age, sex, or comorbidity will be applied.

Patients who have their first recorded prescription for cilostazol during the eligibility period (6 months of continuous enrolment in the database) will be excluded as they will not be new users at the start date. In addition, for DUS2, patients who have a recorded prescription for cilostazol at any time before the start will also be excluded.

Patients with records flagged as incomplete or as substandard data quality according to each database-specific quality-control measures will be excluded.

#### **9.2.6 Follow-up**

Each member of the study cohort will be followed from the start date until the first of the following termination dates:

- End of enrolment in the database
- Death
- End of study period (for DUS2, 31 December 2014)

For each member of the study cohort, comorbidity will be assessed for the entire period of data availability before the start date.

### **9.3 Variables**

#### **9.3.1 Use of Cilostazol and Patterns of Use**

The number of new users of cilostazol and the number of prescriptions, packages, and defined daily dose (DDD) will be ascertained overall and by strength, quantity, and year.

Current use of cilostazol will be ascertained according to the days of supply of each prescription for cilostazol. Days of supply of a prescription are defined as the number of days of intended duration of treatment for that prescription. If days of supply of prescriptions are not recorded in some databases, they will be estimated from descriptive analysis of the number of days between consecutive prescriptions.

Current use is defined as the time involving the days of supply of each prescription plus 7 days to allow for a potential delay in the start of treatment.

### **Duration of Use of Cilostazol**

Duration of use refers to the duration of continuous treatment with cilostazol. Duration will be ascertained by the total number of days of supply of consecutive prescriptions, defined as those prescribed within a maximum interval of 60 days of each other. Sensitivity analyses will be conducted for a maximum interval of 90 days between prescriptions.

### **Daily Dose of Cilostazol**

Daily dose of cilostazol will be calculated using the recorded information on strength and quantity prescribed and the days of supply of each prescription.

### **9.3.2 Characterisation of New Users—Overview**

Characterisation of new users of cilostazol will include the following assessments:

- Characterisation at the start date
  - Demographics, comorbidity, comedications
- Concurrent use of medications
  - Medications that may interact with cilostazol
  - Selected antithrombotic agents
  - Use of platelet aggregation inhibitors
- Characterisation for risk minimisation measures
  - Restricted target population and other changes in the SmPC
- Assessment of contraindications
- Indications associated with treatment and off-label prescription
- Speciality of prescribers

Comorbidity and use of medications will be assessed through the codes for diagnoses, procedures, and medications specific to each database (Table 3).

**Table 3. Types of Diagnosis, Procedure, and Medication Codes in the Study Databases**

Type of Code	IACS, Spain	SIDIAP, Spain	GePaRD, Germany	THIN, UK	National Databases, Sweden
Diagnoses	Hospital: ICD-9 Primary health care: ICPC	ICD-10	ICD-10-GM	Read	ICD-10
Procedures	ICD-9	—	Hospital: OPS Ambulatory: EBS	Read	ICD-9
Medications	ATC	ATC	ATC	Multilex, British National Formulary	ATC

ATC = Anatomical Therapeutic Chemical; EBS = ambulatory operation or procedure codes; GePaRD = German Pharmacoepidemiological Research Database; IACS = Aragón Health Sciences Institute; ICD-10 = International Statistical Classification of Diseases and Related Health Problems, 10th Revision; ICD-10-GM = International Statistical Classification of Diseases and Related Health Problems, 10th Revision, German Modification; ICD-9 = International Classification of Diseases, 9th Revision; ICPC = International Classification of Primary Care; OPS = hospital operation or procedure codes; SIDIAP = Information System for the Advancement of Research in Primary Care; THIN = The Health Improvement Network; UK = United Kingdom.

Source: See Section 9.4.

### 9.3.3 Characterisation of New Users at the Start Date

New users of cilostazol will be characterised at the start date according to demographic, family history, comorbidity, and comedications. Comorbidity will be ascertained through primary care and/or hospital discharge diagnosis codes recorded in the study databases at any time before the start date. Comedications will be ascertained through medication codes recorded in the 6 months before the start date.

Some variables may not be available in all databases. For example, smoking status is available only in THIN, and the recording of data may be incomplete.

The following variables will be assessed:

#### Demographics and Lifestyle Habits

- Age
- Sex
- Calendar year of the start date
- Socioeconomic indicators (proxies: patient's postal code, zip code level)
- Smoking status

#### Family History

- Cardiovascular diseases

## Comorbidity

Comorbidity will be ascertained through diagnosis codes recorded at any time before the start date.

Note: ICD-10 codes in Table 4 will be mapped to ICD-9, ICD-10-GM, and Read codes.

**Table 4. Diagnostic Codes for Comorbid Conditions**

Disease Description	ICD-10
A. Cardiovascular diseases and procedures	All codes in Section A
Diseases of arteries, arterioles, and capillaries	I70-I79
Intermittent claudication	I73.9
Other peripheral arterial disease	I70.2, I70.9, I73.1-I73.8
Atherosclerosis	I70
Other diseases of arteries, arterioles, and capillaries	I74.4
Revascularisation procedures	List of codes to be developed according to each database dictionary
Cardiovascular disease other than diseases of arteries, arterioles, and capillaries	All codes in this section, Cardiovascular disease other than diseases of arteries, arterioles, and capillaries
Ischaemic heart disease	I20-I25
Acute myocardial infarction	I21
Unstable angina pectoris	I20.0
Other acute or subacute ischaemic heart disease	I22,I23,I24
Angina pectoris	I20.1-I20.9
Chronic ischaemic heart disease	I25
Old myocardial infarction	I25.2
Coronary reperfusion surgery and procedures	List of codes to be developed according to each database dictionary
Arrhythmias	I47, I48, I49
Paroxysmal tachycardia	I47
Ventricular tachycardia	I47.0, I47.2
Supraventricular tachycardia and unspecified	I47.1, I47.9
Atrial fibrillation and flutter	I48
Other cardiac arrhythmias	I49
Ventricular fibrillation and flutter	I49.0
Other cardiac arrhythmias	I49.1-I49.9
Cardiac arrest	I46
Conduction disorders	I44-I45
Heart failure	I50
Cerebrovascular disease	I60-I69
Cerebral haemorrhage (subarachnoid, intracerebral, other nontraumatic)	I60, I61, I62

Disease Description	ICD-10
Ischaemic stroke	I63, I64, G46.5
Cerebral infarction	I63
Stroke, NOS	I64
Pure motor lacunar syndrome	G46.5
Sequelae of cerebrovascular disease	I69
Other cerebrovascular disease	I65-I69
TIA	G45
Hypertension and hypertensive heart disease	I10-I15
Hypotension	I95
Other form of heart diseases	I00-I09, I30-I43
Disorders of lipoprotein metabolism and other lipidaemias	E78
B. Bleeding disorders	Any code in Section B
Cerebral haemorrhage	I60, I61, I62
Gastrointestinal bleeding	Any code in the section Gastrointestinal bleeding
Gastroduodenal bleeding	Any code in the section Gastroduodenal bleeding
Gastroduodenal ulcer	K25.0, K25.2, K25.4, K25.6, K26.0, K26.2, K26.4, K26.6, K27.0, K27.2, K27.4, K27.6, K28.0, K28.2, K28.4, K28.6
Gastrointestinal bleeding unspecified	K92.0-K92.2
Acute haemorrhagic gastritis	K29.0
Oesophageal bleeding	K22.6, K22.8 , I85.0
Lower gastrointestinal bleeding a	K62.5, K66.1, I84.1, I84.4, I84.8
Genitourinary bleeding a	N02, R31, N92, N93
Other site bleeding b	I31.2, M25.0, R04
C. Blood dyscrasias	Any code in Section C
Haemolytic anaemias	D55-D59
Aplastic anaemia	D61.9
Acute posthaemorrhagic anaemia	D62
Other anaemias	D60, D61.0-D61.8, D63, D64
Thrombocytopenia	D69.6
Purpura and other haemorrhagic conditions	D69.0-D69.5, D69.8, D69.9
Haemorrhagic thrombocythaemia	D47.3
D. Renal diseases	Any code in Section D
Renal failure	N17-N19
Other renal diseases	N00-N08, N10-N16
Other disorders of kidney and ureter	N25-N39
E. Skin and subcutaneous tissue disorders	Any code in Section E
Dermatitis and eczema	L20-L30

Disease Description	ICD-10
Stevens-Johnson syndrome	L51.1
Toxic epidermal necrolysis	L51.2
Urticaria and erythaema	L50, L51.0, L51.8, L51.9, L52-L54
F. Other conditions	
Peptic ulcer disease	K25-K28
Liver disease	K70-K77
Diabetes mellitus	E10-E14
Chronic obstructive pulmonary disease (COPD), emphysema, respiratory insufficiency	J40-J44, J96
Asthma	J45, J46
Rheumatoid arthritis and other inflammatory arthropathies	M05-M14
Systemic connective tissue diseases	M30-M36
Malignancy	C00-C97
Human immunodeficiency virus disease	B20-B24

ICD-10 = *International Statistical Classification of Diseases and Related Health Problems, 10th Revision*.

a K62.5 = Haemorrhage of rectum and anus; K66.1 = Haemoperitoneum; I84.1 = Internal haemorrhoids with other complications; I84.4 = External haemorrhoids with other complications; I84.8 = Unspecified haemorrhoids with other complications; N02 = Recurrent and persistent haematuria; R31 = Unspecified haematuria; N92 = Excessive, frequent and irregular menstruation; N93 = Other abnormal uterine and vaginal bleeding.

b I31.2 = Haemopericardium, not elsewhere classified; M25.0 = Haemarthrosis; R04 = Epistaxis.

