### **9.7.2 Characterisation of Users at the Start Date**

Analysis Tables 8 and 24: Comorbidity at the start date. Users of cilostazol will be characterised according to the presence of comorbidity at any time before the start date. Comorbidity will be assessed for each disease/condition detailed in Table 4 (Section 9.3.3). The number and percentage of users with comorbidity at the start date will be calculated by sex and age group (< 70 years, ≥ 70 years). The distribution of users by socioeconomic indicators will be calculated (Analysis Table 24).

Analysis Table 9: Comedications at the start date. Users of cilostazol will be characterised according to the use of other medications within 6 months before the start date. Comedications to be assessed are those listed in Table 5 (Section 9.3.3). The number and percentage of users treated with other medications at the start date will be calculated by sex and age group (< 70 years, ≥ 70 years).

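### A few aggregate and residual rows of Table 4 do not match their labels or parents, so those rows of Analysis Table 8 are wrong as coded

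*Protocol*

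**What the plan says.** Section 9.7.2 of the protocol sends Table 4 straight into the results: "Comorbidity will be assessed for each disease/condition detailed in Table 4 (Section 9.3.3" is the instruction, and "The number and percentage of users with comorbidity at the start date will be calculated by sex and age group" is the output, in Analysis Table 8.

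Table 4 (Section 9.3.3) lists diagnoses by ICD-10 code. Four parts of it matter here.

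- **Aggregates.** The total for cardiovascular diseases and procedures is defined as "All codes in Section A". The subtotal for non-arterial cardiovascular disease is "All codes in this section, Cardiovascular disease other than diseases of arteries, arterioles, and capillaries". The last row before Section B is "Disorders of lipoprotein metabolism and other lipidaemias", code E78.
- **Arterial block.** The parent is I70-I79. Its rows are intermittent claudication (I73.9), other peripheral arterial disease ("I70.2, I70.9, I73.1-I73.8"), atherosclerosis (I70), a residual row for other arterial disease (I74.4), and revascularisation procedures, whose codes are still to be developed.
- **Cerebrovascular block.** The parent is I60-I69. The ischaemic stroke row is I63, I64 and G46.5. "Sequelae of cerebrovascular disease" is I69.
- **Residual cerebrovascular row.** "Other cerebrovascular disease" is I65-I69.

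The protocol does not say that the rows exclude one another or add up to their parents.

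**The concern.** A reader of Analysis Table 8 takes each row at its label. A residual row should hold what the named rows leave out, a subgroup should lie inside its parent, and a cardiovascular total should count users with cardiovascular disease. In a few places the printed codes do not do this.

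Baseline comorbidity is a primary objective (Section 8). The amendment table says the cardiovascular categories were refined in Version 2.1 to give more detail. The non-arterial subtotal has a particular use: it separates cardiovascular comorbidity from the arterial disease for which cilostazol is prescribed. If lipid disorders enter it, that separation is blurred. Table 4 is also mapped to the other coding systems, so a wrong grouping passes into every database.

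**Working it through.** The plan gives no figure to reproduce. The check is to expand each printed range and compare each parent with the union of its rows.

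1. **Arterial block.** The named rows cover all of I70 and I73.1-I73.9. Removing these from I70-I79 leaves I71, I72, I73.0 and I74-I79. The residual row holds only I74.4. On the numeric range, seven of the ten three-character categories (I71, I72, I75, I76, I77, I78, I79) have no subgroup, and neither do I73.0 or any of I74 except I74.4. These users still count in the I70-I79 parent, but the residual row understates what its label promises.

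2. **G46.5.** It is in the ischaemic stroke row and not in I60-I69. A user with G46.5 and no I60-I69 code is in the subgroup but not in the parent. The Section A total still includes that user, because it takes every listed code.

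3. **E78.** It is printed within Section A, so it counts towards the Section A total. No header separates it from the preceding rows of the non-arterial block, so by row order it counts towards that subtotal too.

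4. **I69.** It lies in both the sequelae row and the residual cerebrovascular row. The I60-I69 parent is unaffected, since a user counts once. I70.2 and I70.9 overlap in the same way: they are in other peripheral arterial disease and in atherosclerosis (I70).

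5. **Control blocks.** The ischaemic heart disease rows (I20.0, I20.1-I20.9, I21, I22-I24, I25) partition I20-I25 exactly. I47, I48 and I49 cover the arrhythmia parent exactly. The table does hold together elsewhere.

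**Direction and size of the E78 effect.** Let p be the share of users with another non-arterial cardiovascular code and q the share with E78. The subtotal rises by the share with E78 and no other code in the block. If the two are independent, that is (1 − p) × q. The documents give neither p nor q, so these values are assumptions:

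| p | q | Rise in subtotal |
|---|---|---|
| 0.9 | 0.2 | 0.1 × 0.2 = 2 points |
| 0.7 | 0.4 | 0.3 × 0.4 = 12 points |
| 0.5 | 0.6 | 0.5 × 0.6 = 30 points |
| 0.4 | 0.6 | 0.6 × 0.6 = 36 points |

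The spread from 2 to 36 points shows only that the answer depends on the inputs. If E78 tends to occur with the other conditions, the rise is smaller. The Section A total can rise no more than the subtotal, because it contains every non-arterial code and also the arterial ones, including I73.9, the intermittent claudication code.

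**The case against.** The strongest reply is that Table 4 is a list of overlapping descriptors and not a partition. I25.2 sits inside I25, I49.0 inside I49, and I60-I62 appear in both Section A and Section B. On that view I69 in two rows is ordinary nesting. E78 may have been grouped with cardiovascular disease on purpose, and its own row shows its frequency. The text as available has lost its indentation, so E78's place under the non-arterial subtotal is inferred from row order. Nobody drops out of the I70-I79 parent, and G46.5 matters only for users with no I60-I69 code.

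Much of this stands. The I69 overlap is an error only if the rows are meant to be exclusive, which the protocol does not say. The subtotal point is the natural reading and not a certainty.

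Three things survive. Nesting cannot explain a residual row that omits most of its label, or a subgroup that falls outside its parent. E78's membership of Section A does not depend on indentation. If that grouping is deliberate, neither the label nor the aggregate definition says so.

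A reader might go further and infer that the comorbidity percentages in Analysis Table 8 are wrong in general. The protocol does not support that: rows with explicit codes, such as I21, I48, I50 and E78 itself, return what they print. Nor can a particular percentage-point inflation be claimed, since every prevalence above is assumed.

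**Conclusion.** The point holds for a small set of rows. As coded, the residual arterial row is too narrow, the cerebrovascular parent misses users whose only relevant code is G46.5, and the Section A total counts lipid-only users as having cardiovascular disease. The non-arterial subtotal does so as well if row order reflects the nesting. The residual cerebrovascular row needs either a narrower range or a note that it overlaps the I69 row.

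The direction is clear: excluding E78 can only lower the aggregates or leave them unchanged. The size is unknown on the documents. The consequence is limited, because the contraindication and risk-minimisation analyses (Sections 9.7.5 to 9.7.7) rest on specific conditions such as unstable angina, myocardial infarction, arrhythmias and heart failure, and not on these rows. This is a minor correction to the reporting of a primary descriptive objective.

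**What to change.** In Table 4:

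- Set the residual arterial row to the I70-I79 codes outside the named rows: I71-I72, I73.0 and I74-I79.
- Add G46.5 to the cerebrovascular parent. State at the same time whether TIA (G45, also outside I60-I69) is meant to belong to that parent.
- Keep E78 as its own row but exclude it from the Section A total and the non-arterial subtotal, or report both with and without it.
- Set the residual cerebrovascular row to I65-I68, or footnote its overlap with the I69 row. Footnote the I70.2 and I70.9 overlap with I70 in the same way.

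Carry the edits into the mappings to the other coding systems. Apply the same definitions to DUS2 and to a rerun of the affected DUS1 rows, or show old and new definitions side by side in DUS2. Changing DUS2 alone would break the comparison that Section 9.3.6 plans.

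No new data are needed. The rerun is small but not free: Section 6.1 reports DUS1 already complete in THIN, IACS, SIDIAP and Sweden as of 30 January 2015, so finished analyses would have to be reopened. The side-by-side display in DUS2 avoids this. The cardiovascular subtotal can be expected to come out lower.
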